### **i) Provisions to Monitor the Data to Ensure the Safety of subjects**

A formal Data Safety and Monitoring Board (DSMB) will be utilized. The DSMB is already established and is operating through the NIH-funded ACISR center grant at Zucker Hillside Hospital (ZHH).

The membership includes 2 physician researchers who are not involved with the current trial but have experience in clinical trials in psychiatric samples, as well as other senior faculty in the Division of Psychiatry Research at ZHH. In collaboration with the primary statistician for this trial ([name]; ISMMS Co-I), the DSMB will be asked to review data on this trial at any time that there is a serious adverse event, reportable to the Institutional Review Board (IRB) and every 6 months following study start up (regardless of site). In addition to the DSMB, the PI at each site will review safety data in real time to address any concerning adverse events.

***MSSM Additional Monitor:***

*Indicate whether this person is the PI, a Team Member, or is Independent: Team Member (co-investigator)*

*Last Name: [name]*

*First Name: [name]*

*Academic Title: Associate Professor*

*Department: Psychiatry*

*Mailing Address: [name]*

*[contact]*

*[contact]*

*E-mail: [contact]*

*2. [name] has been responsible for running two previous studies using this agent in bipolar disorder (Goldberg et al 2004; [name] et al 2012).*

*3. Adverse events, subject compliance with the protocol, and drop outs will be monitored for safety.*

*4. **ACCUMULATED** safety and data information (items listed in number 3 above and interim analysis of efficacy outcomes) will be reviewed by the monitors or the Data Monitoring Committee (DMC) twice a year.*

*5. Alteration of the study design is not expected; however, SAEs will be considered for unblinding and relatedness to drug will be assessed.*

*6. In order to minimize toxicity we are only allowing up to a max of the FDA recommended dose – dosing is flexible based on AEs and tolerability.*

*7. There will be no specialized grading system used to evaluate adverse events.*

*8. Procedures that will be used to assure data accuracy and completeness include double data entry and frequent queries of database.*

*9. Should a temporary or permanent suspension of your study occur, in addition to the PPHS, we will report the occurrence to NIH as well as ZHH, the other site conducting study.*

|   |   |  |
|---|---|--|
|  | Protocol Title:                           | 1/2-Pramipexole in Bipolar Disorder: Targeting Cognition (PRAM-BD) |
|   | Principal Investigator Name/Contact Info: | [name]   |
|   | Primary Contact Name/Contact Info:        | [name]
[contact]                          |
|   | Date Revised:                             | March 23, 2016 – date of IRB approval May 6, 2017                  |
|   | Study Number:                             | GCO 13-0237, HS 14-00328   |

## j) Withdrawal of Subjects

Participants with an exacerbation of mania/depression (YMRS  $\geq$  15 or HRSD  $\geq$  18) will be discontinued and treated by the study physician. Suicidal ideation will be assessed at each visit with the Columbia Suicide Severity Rating Scale (C-SSRS). Significant suicidal ideation will be addressed immediately using the standard clinical response at ISMMS (evaluation at the walk-in clinic for potential need for hospitalization). Participants at risk for suicidal behavior will be discontinued. Side effects will be rated by a study physician at each visit. Any side effect deemed to be a serious adverse event or an unanticipated follow up will be reported to the PI, and the ISSMS Institutional Review Board (IRB) and appropriate follow up will be conducted. In addition, participants who exhibit an inability to follow the protocol will be discontinued and withdrawn from the study.

To ensure orderly termination from the study, the study physician would meet with the participant to discuss termination and discontinuation of medication. Safety measures would be collected and a follow-up visit by phone would be scheduled to further ensure safe discontinuation. Pramipexole should be tapered off at a rate of 0.75mg per day until the daily dose has been reduced to 0.75mg. Thereafter, the dose should be reduced by 0.375mg per day. We will schedule an in-person follow-up visit by phone to address any remaining concerns the participant may have.

Participants may withdraw from the study for any reason at any time by contacting the principle investigator or any of the research staff. It is also possible to withdraw permission for the use and disclosure of any protected information for research but it must be done in writing to the principle investigator. In the event permission is withdrawn, information that was already collected may still be used if that information is necessary to complete the research study.

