## f) Procedures Involved in the Human Research

All eligible participants will undergo study visits at screening, baseline (week 0), week 1, week 2, week 3, week 4, week 6, week 8, and week 12, (end of study).

Randomization will be conducted via a computer generated program and all study staff will be blinded unless un-blinding is required for safety reasons. Subjects will be randomized on a 1:1 ratio with stratification for concomitant antipsychotic status and depression at baseline (HRSD <8 vs  $\geq$  8). Study drug will be blinded and matched to placebo. Adapting from our previous work in BD and according to package labeling, the dosage titration schedule will be slow and flexible. Dosing will be initiated at 0.25 mg QHS on night one, followed by 0.25 mg BID day two onward, and increased every week to a target of 4.5 mg/day. As compared with our previous maximum 1.5 mg/day ([name] et al. 2012), we opted to allow up to 4.5 mg/day (the maximum approved dosage in Parkinson’s disease) to ensure adequate target engagement. We are familiar with this dose range, as 4.5 mg/day was allowed in our study in BD depression (Goldberg et al. 2004). Dosing will be flexible based on side effects; however, if 1.5 mg/day cannot be tolerated, the subject will be discontinued. Titration will occur up to week 6 and then efforts will be made to maintain the same dose until the completion of the trial (week 12).

Measures are described in detail below:

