**Primary hypothesis testing:** 100 participants will be randomized in a 1:1 allocation to treatment with pramipexole or placebo. The primary assessment of safety will be based on the incident of adverse event rates and standardized mood ratings at each visit. Differences in the incidence of individual adverse events will be compared between randomization arms using Poisson regression. Exact 95% confidence intervals (based on the Poisson distribution) for the risk ratios for individual adverse events for treatment with pramipexole versus placebo will be computed and may incorporate an estimated overdispersion parameter if observed variability exceeds that determined by the Poisson distribution. Performance on the IGT will also be used to track potential changes in impulse-control (baseline, weeks 6 and 12). We will test for correlations between IGT performance and mania symptoms at the times of testing (simultaneous measurements). Moreover, we will use IGT change scores as predictors in regression models to evaluate changes in mania ratings at concurrent time points as well as future time points. This will directly address the question of whether or not changes in IGT strategy serve as markers of current mania and/or impending affective destabilization.

The relative specificity of pramipexole in binding to D2/D3 receptors allows for a unique opportunity to enhance DA in neural networks associated with specific aspects of cognition as well a reward processing, which will be carefully assayed in this study so that exploratory analyses will be able to test questions related to the role for these receptors across several interacting domains in BD, at least at the level of behavior. Exploratory analyses will include specific domains and individual tasks which will be modeled to account for main effects and interactions (as described in primary analyses below).

The primary outcome for efficacy is change in cognition from baseline to week 6 (MCCB Composite). The null hypothesis is that there is no difference in this change between

|   |   |  |
|---|---|--|
|  | Protocol Title:                           | 1/2-Pramipexole in Bipolar Disorder: Targeting Cognition (PRAM-BD) |
|   | Principal Investigator Name/Contact Info: | [name]   |
|   | Primary Contact Name/Contact Info:        | [name]
[contact]                          |
|   | Date Revised:                             | March 23, 2016 – date of IRB approval May 6, 2017                  |

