|   | Study Number:                             | GCO 13-0237, HS 14-00328   |

patients on pramipexole vs. patients on placebo. This will be tested in an intent-to-treat analysis using a 0.05 level two-tailed test based on a mixed effects regression model, with patients considered to be a random effect, and randomization group a fixed effect. In order to preserve statistical power, change in MCCB Composite will be used as the dependent variable; however, secondary analyses will be conducted for MCCB domain scores and measure of reward processing. The use of two post baseline evaluations (weeks 6 and 12) and the ability of the model to incorporate all available data, also improves efficiency (i.e., power). This approach will also be employed in subsequent comparisons of specific domains and for measures of reward processing. These additional analyses will be conducted at a nominal 0.05 level and will focus on enhancing interpretation of the primary analysis by highlighting the specific domains most affected by pramipexole. Since randomization is stratified by concomitant antipsychotic use and baseline depression status, indicators of stratification will be included in the model as fixed effects.

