*Missing data:* Although the mixed effects modeling approach allows patients with evaluations at week 4 but missing at week 8 to be included, bias may be introduced if missing data are related to patient response. For example, it may be that patients responding poorly are less likely to have a week 8 evaluation than those patients with better response. The mixed effects analysis would weigh the results of these poorly performing patients less (as they provide fewer data) and in the presence of a positive effect of pramipexole, decrease power. To assess the extent that any bias has been introduced by missing data, we will impute missing week 8 values. Note that if no bias is produced by the missing data, analyses with and without imputation should provide virtually identical results. If the analyses produce different results, we will work to identify the causes by comparing patients with and without missing data. Based on our prior trial experience we expect relatively few patients (< 10) to be missing the week-8 visit due to attrition. Patients with missing data will have their 8 week MCCB score imputed via multiple imputation assuming that the data are MAR, i.e., the missing nature of the variable is independent of the value of the variable given the observed data. The specific imputation model to be used will be determined prior to examination of any outcome data, but will include MCCB score at baseline and at 4 weeks. Separate imputations will be done for each randomization group.

*Due to the 12 week course of the study, mixed models will still be utilized for variables collected with sufficient frequency; however, when incorporating missing data, we will only be able to do so when at least two time points are included. Subjects with only baseline data will be included in descriptive analyses but will be dropped for analyses where necessary.*

|   |   |  |
|---|---|--|
|  | Protocol Title:                           | 1/2-Pramipexole in Bipolar Disorder: Targeting Cognition (PRAM-BD) |
|   | Principal Investigator Name/Contact Info: | [name]   |
|   | Primary Contact Name/Contact Info         | [name]
[contact]                          |
|   | Date Revised:                             | March 23, 2016 – date of IRB approval May 6, 2017                  |
|   | Study Number:                             | GCO 13-0237, HS 14-00328   |

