**Sample size/Power:** A total of one hundred patients will be randomized 1:1 (50 from ISMMS, 50 from ZHH). The adequacy of this sample size is based on the ability to reject the null hypotheses of no difference between treatment groups with respect to the MCCB composite score with sufficient power (80%). Ideally, sample size would be determined to ensure adequate power to detect the minimal clinically important difference. No specific guidelines exist to establish such a threshold in this setting but cognitive change of at least a moderate effect would likely be necessary to allow for clinical meaningfulness. Our sample size provides approximately 80% power to detect a standardized difference (e.g., Cohen’s d) of approximately 0.55 with a two-tailed 0.05 level test. For the pre-specified subgroup analysis based on concomitant use at baseline, the detectable standardized difference is about 0.80.

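### The week-6 analysis labelled intent-to-treat can lose patients who stop early, because no MCCB is clearly planned once study drug is stopped

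*Combined protocol and SAP*

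**What the plan says.** Section 5(h), Primary hypothesis testing, makes the week-6 change in MCCB Composite the primary efficacy outcome and states: "This will be tested in an intent-to-treat analysis using a 0.05 level two-tailed test based on a mixed effects regression model". It adds that "change in MCCB Composite will be used as the dependent variable".

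Sections 5(e) and 5(f) schedule the MCCB at baseline, week 6 and week 12 only. Section 5(e) adds a parenthesis to week 12 that refers to the end of the study; section 5(f) describes week 12 itself in those terms.

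Exits are described in three places:

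- Section 5(f), on tolerability: "if 1.5 mg/day cannot be tolerated, the subject will be discontinued". It does not say whether this means from drug or from the study. Titration runs up to week 6.
- Section 5(j): patients with a mood exacerbation or at risk of suicidal behaviour are discontinued, again without saying from what. In addition, "participants who exhibit an inability to follow the protocol will be discontinued and withdrawn from the study". The termination paragraph names safety measures and a telephone follow-up, and no cognitive testing.
- Section 6: participation in the study ends in any case of clear symptom worsening.

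Section 5(h), Missing data, plans multiple imputation of a week-8 MCCB score under MAR, separately by arm, from a model that includes the baseline and week-4 scores. It then says that missing data can be incorporated only when at least two time points exist, and that "Subjects with only baseline data will be included in descriptive analyses but will be dropped for analyses where necessary".

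**The concern.** An intent-to-treat comparison needs an outcome, observed or properly modelled, for every randomised patient whether or not drug was continued. Here the first post-baseline MCCB is at week 6, while titration, and with it the main period for intolerance, fills the weeks before. A patient who leaves in that period has a baseline score and nothing else.

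The reasons for leaving (intolerance, mood worsening, inability to follow the protocol) can all be consequences of treatment and need not be balanced between arms. Section 6 lists confusion and memory problems among the common side effects of pramipexole, so the reason for stopping may overlap with what the MCCB measures. If such patients drop out of the comparison, the estimate moves away from the effect of being assigned to pramipexole. Outcomes that were never collected cannot be recovered at the analysis stage.

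**Working it through.** **1. Who has a primary outcome under the plan as written**

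| Time of stopping | MCCB scores held | In the change-score model? |
|---|---|---|
| Before week 6, leaves the study | Baseline only | No outcome; may be dropped |
| Between weeks 6 and 12 | Baseline, week 6 | Yes, with the primary value |
| Not before week 12 | Baseline, weeks 6 and 12 | Yes |

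The gap is confined to the first row.

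**2. Whether the planned imputation fills it**

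The target is a week-8 score and one predictor is a week-4 score. The MCCB is scheduled at neither visit, so the procedure cannot be run as written. If the weeks were corrected to 6 and 12, imputing within arm under MAR from patients who continued would still estimate what stoppers would have scored had they continued. That is not the effect of assignment.

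**3. The plan's own power figure**

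Inputs from section 5(h), Sample size/Power: "A total of one hundred patients will be randomized 1:1", so 50 per arm; d = 0.55; two-sided 0.05.

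Power = Φ(0.55 × √(50/2) − 1.96) = Φ(2.75 − 1.96) = Φ(0.79) = 0.785 (0.777 with the t distribution). This agrees with the stated figure of about 80%, and it counts all 100 patients. With nine of them lacking an outcome, 91 remain and power is about 0.73 to 0.75, depending on how the losses fall between arms.

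**4. Size of the distortion (illustration)**

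Let q be the fraction of the drug arm lost before week 6 and e the effect those patients would have shown, in SD units. Let d = 0.55 be the effect in those who stay.

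Effect of assignment = (1 − q) × 0.55 + q × e. Overstatement = 0.55 / (effect of assignment) − 1.

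The range of q is an assumption. The upper value follows from the plan's expectation of fewer than 10 missing patients: if all nine were on drug, q = 9/50 = 18%.

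| q | e | Effect of assignment | Overstatement |
|---|---|---|---|
| 10% | 0 | 0.90 × 0.55 = 0.495 | 11% |
| 18% | 0 | 0.82 × 0.55 = 0.451 | 22% |
| 10% | −0.25 | 0.495 − 0.025 = 0.470 | 17% |
| 18% | −0.25 | 0.451 − 0.045 = 0.406 | 35% |

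The rows with e = −0.25 assume no matching loss on placebo. If both arms lose the same fraction and leavers worsen equally, the q × e term cancels and the e = 0 rows apply.

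**5. Under no true effect of assignment**

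Suppose patients are lost from the drug arm only and would have changed by 0.5 SD less than stayers. The apparent difference is q × 0.5, that is 0.05 at 10% loss and 0.09 at 18%. The chance of a significant result favouring drug, nominally 0.025, becomes 0.043 (45 against 50 patients) and 0.062 (41 against 50). With a gap of 0.25 SD and 10% loss it is 0.033. The harm is modest when losses are few or unselective.

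**The case against.** A reader might infer that every patient who stops drug is removed and that the analysis is in truth one of patients who tolerated and followed treatment. The documents do not support that. A patient who stops after week 6 keeps the primary value, and the mixed model uses all available data. Only inability to follow the protocol (section 5(j)) and clear symptom worsening (section 6) are expressly tied to leaving the study; for intolerance and mood exacerbation the text says discontinued and no more. Exclusion of baseline-only patients is qualified, not absolute.

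It can also be said that the end-of-study parenthesis in section 5(e) provides an MCCB at early termination. It may be meant so, but it is attached to week 12, and the termination paragraph lists no cognitive test. It leaves the matter unclear.

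The plan does address missing data: it compares results with and without imputation, and patients with and without missing scores if results differ. That is sound in intent, but it rests on scores that are not scheduled.

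Finally, expected attrition is low and the direction of bias is not established. The plan itself discusses the loss of poor responders as a loss of power. This stands: overstatement is a plausible result, not a demonstrated one, and loss rates above 18% of one arm would go beyond the plan's own expectation.

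**Conclusion.** The point holds in a limited form. The analysis labelled intent-to-treat tends to leave out randomised patients who stop before week 6 and leave the study, for reasons that may be related to treatment. The plan provides no clear cognitive follow-up for them and no workable imputation.

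Within the plan's own expectation on missing data, the effect of assignment could be overstated by 11–22% if drug-arm stoppers gain nothing, and by 17–35% if they worsen by 0.25 SD with no matching loss on placebo. Both ranges rest on assumed loss rates and assumed outcomes in stoppers; the true direction and size depend on how selective and unbalanced the losses are. The change should be made, because the missing scores can only be obtained while the trial is running.

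**What to change.** 1. In sections 5(j) and 6, and by reference in 5(f), distinguish discontinuation of study drug from withdrawal of consent. Leave every clinical stopping criterion as it is. Sections 5(j) and 6 need to change together, or they will contradict each other.
2. Ask patients who have stopped drug and not withdrawn consent to complete the MCCB at the scheduled week-6 and week-12 visits where clinically feasible. State what the end-of-study parenthesis in section 5(e) means.
3. Include those scores in the primary model by randomised arm, and define the analysis set and estimand.
4. Replace the rule for baseline-only patients. A change-score model gives them no outcome, so use either a model with baseline, week-6 and week-12 MCCB all as outcomes, or multiple imputation of the week-6 and week-12 scores that draws on the off-drug data collected.
5. Add a sensitivity analysis that departs from MAR, for example delta-adjusted imputation.

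The cost is a small amendment and some effort to bring patients back; some will decline. Section 11 sets participant payments for these visits ($50 at week 6, $100 at week 12), but the documents show no budget and do not say whether visits after discontinuation are funded. The estimated effect may also be smaller: in the e = 0 scenarios above, with all 100 patients analysed, power is about 0.69 at 10% stopping and 0.61 at 18% (t distribution), against 0.777 at d = 0.55.

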## 6) Risks to Subjects

During the informed consent process, participants will be informed of the potential risks associated with the study. At each weekly visit the study physician will meet with participants and conduct a thorough review of symptoms including mood, and suicidal ideation. If there is an acute worsening of symptoms the study clinicians will review the case with the PI (or will make an emergency decision as needed) to ensure that the participant receives emergency care or hospitalization. Participation in the study will be discontinued in any case of clear symptom worsening. Between weekly visits, the participants will have emergency contact information.

Along with closely monitoring for symptom exacerbation, each visit with the study physician will entail a detailed side effect evaluation, which will include vital signs and a

|   |   |  |
|---|---|--|
|  | Protocol Title:                           | 1/2-Pramipexole in Bipolar Disorder: Targeting Cognition (PRAM-BD) |
|   | Principal Investigator Name/Contact Info: | [name]   |
|   | Primary Contact Name/Contact Info:        | [name]
[contact]                          |
|   | Date Revised:                             | March 23, 2016 – date of IRB approval May 6, 2017                  |
|   | Study Number:                             | GCO 13-0237, HS 14-00328   |

side effect checklist. The most common side effects of pramipexole are nausea, headache, dizziness, insomnia, constipation, muscle weakness, abnormal dreams, confusion, memory problems, urinary frequency. Participants will be educated about the potential for these side effects. Rare side effects have also been reported including sedating effects, impulse control symptoms (e.g. gambling), hallucinations, and orthostatic hypotension. The informed consent process will alert participants to these potential risks and close monitoring will ensure prompt response to any adverse effects with appropriate treatment and/or study discontinuation, as indicated.

